6.5 POOLING OF CENTRES

This section is not applicable because centre/country is not included in the statistical model.

6.6 HANDLING OF MISSING DATA AND OUTLIERS

For each time to event analysis, patients who do not experience the assessed outcome will be censored.

Missing or incomplete AE dates are imputed according to BI standards (see “Handling of missing and incomplete AE dates”) [3]. The same philosophy will be applied to missing or incomplete outcome event dates, index qualifying stroke date, concomitant medication dates (where applicable), and dates of temporary study medication discontinuation and restart, and trial completion date.

If prior _____ is missing, it will be assumed that the patient did not have previous _____ when used as a baseline covariate in the Cox model. If baseline creatinine clearance is missing, then the first on-treatment creatinine clearance will be used as a baseline covariate in the Cox model (and if there is no creatinine clearance in the database, then creatinine clearance ≥ 50 will be used as covariate in the model).

For NIHSS –if the score on any item is 9 or the ataxia item is missing, default these items to “0” (best case). Otherwise, for patients with up to 2 items missing, the worst case score for that item is imputed. For patients with 3 or more items missing, a total score will not be calculated and the NIHSS will be considered missing.

Other missing and incomplete data will not be imputed.

6.7 BASELINE, TIME WINDOWS AND CALCULATED VISITS

The planned study period will include 14 visits conducted at Screening, Randomization (Day 0, i.e., baseline), and every 3 months thereafter during the first year. After year one, planned visits will be every 6 months starting month 18 with telephone follow ups at months 15, 21, 27 and 33.

If the trial is extended, planned visits will be extended at 3 month intervals. If a patient stops medication before the end of the trial, visits should still be made to the clinic (or by telephone). For patients that permanently stop study drug and choose not to continue visits, vital status will be checked during the trial closeout.

Table 6.7: 1 Visit schedule

Visit	1	2	3	4	5	6	7	8	9	10	11	12	13	14
Month	-	0	3	6	9	12	15	18	21	24	27	30	33	36

The actual number of visits that a patient will have depends on when the patient started the trial.

Time windows will not be used. Most analyses are collected in real time (e.g., time to death). Variables that are collected at visits will be analyzed by planned time point.

A patient will be considered to have completed follow-up if he/she has a date of last contact during the end of trial period, defined as within six months of the date of Last Patient Out.

6.8 CALCULATION OF TIME TO EVENT

The calculations of time to events and the time that patients without an event were in the study (under risk) are done according to procedures described in this section.

Date of randomization

The day of randomization is the reference for all RS analyses, regardless of when (or if) treatment started.

Date of event

For one-time events, like death, the date of event reported on the event case report form (CRF) will be used. For events with multiple episodes, such as MI and recurrent stroke, the onset date of the first episode will be used. For composite outcome, the onset date of the first occurring component will be used.

Date of last contact

This is determined as the latest date among the trial completion date (from CRF), last clinic visit/phone call, assessment date or last known alive date from the vital status CRF, and the maximum of the start dates of all adverse events. If a patient dies, then the date of death is the date of last contact.

Survival time for full follow-up analyses

For those *with an event*, the survival time is calculated as:

$$\langle \text{date of event} \rangle - \langle \text{date of randomization} \rangle + 1$$

For those patients *without an event*, the survival time is calculated as:

$$\langle \text{date of last contact} \rangle - \langle \text{date of randomization} \rangle + 1$$

Survival time for on-treatment analyses

For those *with an event*, the survival time is calculated as:

$$\langle \text{date of event} \rangle - \langle \text{treatment start date} \rangle + 1$$

For those *without an event*, the survival time is calculated as:

$$\langle \min(\text{date of last administration of trial medication} + 6, \text{date of last contact}) \rangle - \langle \text{treatment start date} \rangle + 1$$

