7.3 PLANNED ANALYSES

Two patient populations are defined:

- The randomized set (RS) consists of all patients who were randomized, regardless of whether they took study medication. The start date of the observation period for this population is the date of randomization.
- The treated set (TS) consists of all patients who were treated with at least one dose of study medication. The start date of the observation period for this population is the date of first intake of trial medication.

Two follow-up periods are defined:

- Full follow-up: until the end of the trial, including all observed time on and off trial medication until the last known alive date (or date of death)
- On-treatment: until the date of discontinuation of trial medication + 6 days

When composite endpoints are evaluated as survival endpoints, the time to first onset date of any of the events listed in the composite endpoint will be used as the date of the event. For

combined endpoints of nonfatal and fatal events the time to the first event is taken. If the fatality is the first event, then the time to death (not the time to the event leading to death) is taken.

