7.3.1 Primary analyses

The primary endpoint is time to first recurrent stroke (ischemic, hemorrhagic, or unspecified) as determined by the adjudication committee. It will be analyzed using the Cox proportional hazards regression model. Covariates included in the model will be age (binary, $<$ or \geq 75 years), renal impairment (binary; creatinine clearance $<$ or \geq 50 mL/min), and stroke or TIA prior to index stroke (binary, “yes” or “no”).

The primary analysis will be performed on the RS for the full follow-up period. Patients who discontinue study medication will be followed until the end of the trial for OEs including vital status. Patients who are lost to follow-up for vital status will be censored for the primary endpoint of recurrent stroke at the time of their last known alive date.

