7.4 HANDLING OF MISSING DATA

A major goal of the trial is to obtain virtually complete follow-up of vital status and all other OEs. As mentioned in [Section 7.3.1](#), all patients lost to follow-up will be treated as censored at the time of last known vital status.

No missing data will be imputed for the primary and secondary time to event endpoints. Regarding covariates for the Cox model, age and creatinine clearance are mandatory for trial entry, so these variables will not be missing. If prior stroke or TIA data are missing, the patient will be assumed to have no stroke or TIA prior to index stroke (for the purpose of inclusion into the analysis only), thus no covariate data will be missing for purposes of analyzing the Cox model.

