6.3 PATIENT SETS ANALYSED

- Screened set (SCR):
This patient set includes all patients who signed informed consent and completed at least some screening procedures.
- Randomized set (RS)
This patient set includes all randomized patients, whether treated or not.
- Treated set (TS):
This patient set includes all patients who were documented to have taken at least one dose of investigational treatment. The start date of the observation period for this analysis set is the date of first intake of trial medication.

The final decision as to whether a patient is included in or excluded from each analysis set will be taken before database lock in a blinded manner and will be documented in the minutes of the Blinded Report Planning Meeting (BRPM) or Database Lock Meeting.

Analyses will be performed as outlined in [Table 6.3: 1](#).

Table 6.3: 1 Patient sets analysed

Class of endpoint	Patient set		
	Screened set	Randomized set	Treated set
Primary endpoints		X	S ¹
Secondary endpoints		X	
Safety endpoints		S ¹	X
Patient disposition	X		

¹ S=Sensitivity analyses (see [Section 7.4](#) and [7.8](#))

Two analysis periods are defined:

- Full follow-up: from date of randomization until the date of last contact (see [Section 6.8](#)), including all observed time on and off trial medication
- On-treatment: from the date of first treatment intake until the date of discontinuation of trial medication + 6 days (or death, if death occurs earlier)

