7.4 PRIMARY ENDPOINTS

The primary endpoint of time to first recurrent stroke (ischemic, hemorrhagic, or unspecified) as determined by the adjudication committee will be analyzed using the Cox proportional hazards regression model. Covariates included in the model will be age (binary, < or ≥ 75 years old), renal impairment (binary; creatinine clearance < or ≥ 50 mL/min), and stroke or TIA prior to index stroke (binary, “yes” or “no”).

The primary analysis will be performed on the RS for the full follow-up period. Patients who discontinue study medication will be followed until the end of the trial for OEs including vital status. Patients who are lost to follow-up for vital status will be censored for the primary endpoint of recurrent stroke at the date of last contact (see [Section 6.8](#)).

The hypotheses for the primary (and key secondary endpoints) are:

$$H_0: HR_{\text{Dabigatran/ASA}} = 1 \quad \text{vs.} \quad H_a: HR_{\text{Dabigatran/ASA}} \neq 1$$

Tests will be performed at the two-sided $\alpha = 0.05$ level.

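### Censoring at a last-known-alive date counts unassessed time as stroke-free; the hazard ratio is affected only if that time differs between arms

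*SAP*

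**What the plan says.** The rule is stated consistently. SAP 6.3 runs full follow-up "from date of randomization until the date of last contact". SAP 6.8 defines that date as the latest of several, including "last clinic visit/phone call, assessment date or last known alive date from the vital status CRF". SAP 7.4 says that patients lost to follow-up for vital status "will be censored for the primary endpoint of recurrent stroke at the date of last contact". Protocol 7.3.1 has them "censored for the primary endpoint of recurrent stroke at the time of their last known alive date", and Protocol 7.4 says "all patients lost to follow-up will be treated as censored at the time of last known vital status". The same date serves every full follow-up endpoint, fatal or not.

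The protocol also foresees patients who are known to be alive but whose stroke status is unknown:

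- Section 6.2.2 lists five levels of reduced participation. The fourth still collects outcome events at the end of the trial; the fifth collects vital status alone.
- Section 6.2.3.4, for patients who cannot be reached directly, makes vital status the minimum and asks for recurrent stroke only if it can be obtained.
- Section 6.2.3.5 permits vital status from records or public databases after full withdrawal of consent.

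On closeout, SAP 6.7 says: "For patients that permanently stop study drug and choose not to continue visits, vital status will be checked during the trial closeout". On completeness it says: "A patient will be considered to have completed follow-up if he/she has a date of last contact during the end of trial period", meaning within six months of last patient out.

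**The concern.** Knowing that a patient is alive does not show that the patient has had no stroke. A last-known-alive date is the right censoring date for all-cause death. It is not right for stroke, ischemic stroke, disabling stroke or the composite of stroke, MI and cardiovascular death, unless outcome events were also ascertained up to that date. Where they were not, the interval enters the risk set as stroke-free time. In effect this fills in no stroke, although Protocol 7.4 says nothing is imputed for these endpoints.

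At stake are the absolute stroke rates and, if the arms differ, the primary hazard ratio. Because completed follow-up is defined by the same date, a patient found alive in a database at closeout counts as complete even if stroke was last assessed long before.

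**Working it through.** **Inputs from the plan.** Two-sided alpha 0.05; 353 events; HR 0.70; 3000 patients per arm; 2.5 years of recruitment and 3 years in total (Protocol 7.6). Yearly rates are 7.4% in months 1-6, 3.2% in months 7-12 and 2.5% after that (Table 7.6:1). Follow-up is taken as uniform over 6 to 36 months; its mean, (6 + 36)/2 = 21 months, matches Protocol 3.1.

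**Reproducing the plan.** Power = Phi(|ln HR| × sqrt(353)/2 − 1.96). At HR 0.70: 0.3567 × 9.394 − 1.96 = 1.391, so 91.8% (plan: about 92%). Expected strokes per arm = 3000 × the integral of h·λ(t)·exp(−h·Λ(t))·P(follow-up > t), where λ is the yearly rate, Λ its cumulative sum, and h is 1 for ASA and 0.70 for dabigatran. This gives 206.2 + 146.0 = 352 (plan: 353).

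**Assumptions not in the plan.** A share q of each arm is followed for vital status only from a uniformly random point in the patient's follow-up, and strokes after that point are not seen. Under these hazards an affected patient then loses a fraction 0.38 of the strokes that full follow-up would show. The fraction is 0.22 if ascertainment stops 6 months before the end, 0.45 if 12 months before, and 1.00 if at randomization.

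**Effect of the current rule.** To a close approximation the HR is multiplied by (1 − 0.38·q_DE)/(1 − 0.38·q_ASA). For 10% against 5% this is 0.962/0.981 = 0.981; for 2% against 1% it is 0.9924/0.9962 = 0.996. Solving the expected Cox score equation gives:

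| DE / ASA share | True 1.00 reads | True 0.70 reads |
|---|---|---|
| 5% / 5% | 1.000 | 0.700 |
| 2% / 1% | 0.996 | 0.697 |
| 3% / 1% | 0.992 | 0.695 |
| 10% / 5% | 0.980 | 0.686 |
| 5% / 10% | 1.020 | 0.714 |

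A simulation with the same inputs gives 0.980, 0.687 and 0.714 for the 5-point imbalances. For 2% against 1%, the range over stopping patterns is 0.998 to 0.990.

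**Strokes not seen, HR 0.70.** 2% DE / 1% ASA: 0.38 × (0.02 × 146.0 + 0.01 × 206.2) = 1.9. 10% DE / 5% ASA: 0.38 × (14.6 + 10.3) = 9.5.

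**Error and power.** With d = |ln factor| × 9.394, the two-sided type I error is 5.02% (2% / 1%) or 5.41% (10% / 5%). The part in favour of dabigatran, when it has the excess, is 2.7% or 3.8% instead of 2.5%. If ASA has the excess, power falls from 91.8% to 91.2% (HR reads 0.703) or 88.5% (0.714).

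**If 60% of the later strokes surface.** The lost fraction becomes 0.38 × 0.4 = 0.152. The factor is 0.9848/0.9924 = 0.992 at 10% / 5% and 0.998 at 2% / 1%.

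**Alternative rules, 10% / 5%, true HR 1.00, 60% surfacing.** Current rule: 0.992. Censoring early but counting the late events: 1.012, a larger error in the opposite direction. Censoring early and leaving the late events out: 1.000.

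**The case against.** The case on the other side is substantial.

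1. The rule is deliberate and agrees between protocol and SAP. The trial is double-blind, and every effect on the HR needs an imbalance for which the documents give no evidence.
2. The group should be small. Protocol 7.4 aims at nearly complete follow-up of vital status and outcome events. Sites are to ask patients who miss the final visit about outcome events as well (6.2.3.4). Patients are asked to choose the fullest follow-up they accept (6.2.2), and complete withdrawal is called rare (6.2.3.5). Deaths are adjudicated, so some fatal strokes would surface. The CRF is not shown, and a date on the vital status form need not mean that stroke went unassessed.
3. The remedy can do harm. Leaving out strokes or cardiovascular deaths that surface late sets aside known adjudicated events, while Protocol 3.3.4.1 says that data from all randomized patients are used. Counting them while censoring others earlier creates the opposite bias. The same care is needed for events reported between visits.
4. The primary rule could be left alone and a sensitivity analysis added.

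Points 1 and 2 limit the size but do not make a last-known-alive date informative about stroke. Point 3 stands and shapes the fix. Point 4 is a reasonable fallback, but the primary estimate would still rest on time that nobody assessed.

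**Conclusion.** The rule is wrong for non-fatal endpoints wherever only vital status is known, and the protocol allows that state. If such patients exist and some of their strokes never surface, stroke rates are understated, by about 0.4% for each 1% of patients affected. The HR moves only with an imbalance: 0.4% at 2% against 1% and 2% at 10% against 5%, on assumed shares and with no later stroke surfacing. For scale, the pessimistic 0.714 is close to the 0.711 that Protocol 7.6 tabulates for AF switching and regards as of limited impact. Severity is low to moderate.

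Stronger readings that the documents do not support:

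- That the primary HR is biased, or the type I error materially inflated. This needs unequal shares, and none are given.
- That rates are certainly understated in both arms. This depends on such patients existing in each arm and on their strokes staying unseen.
- That everyone who stops drug or visits is wrongly censored. Patients who still report outcome events are handled correctly, and the on-treatment rule (last dose plus 6 days) largely avoids the problem.
- That no sensitivity analysis exists. Parts of the SAP are not visible, although a sensitivity analysis would not change the stated primary rule.

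The completeness point in SAP 6.7 holds whatever the effect on the HR, because the reported figures would not reveal the gap.

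**What to change.** Before unblinding, amend SAP 6.7, 6.8 and 7.4, with matching text in Protocol 7.3, 7.3.1 and 7.4:

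1. For stroke, ischemic stroke, disabling stroke and the stroke/MI/cardiovascular-death composite, censor event-free patients at the last date outcome-event status was ascertained: clinic visit, phone call, or documented proxy or record review. Keep last known alive for all-cause death.
2. State in advance how events first learned of after that date are handled, so that events and event-free time are treated alike. Reconcile this with Protocol 3.3.4.1. State that all adjudicated strokes still count towards the 353-event target.
3. Run the current last-known-alive rule, with all adjudicated events counted, as a sensitivity analysis.
4. Report vital-status-only person-time and completeness of stroke follow-up by arm. In SAP 6.7, base completed follow-up for stroke on the ascertainment date.

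The cost is one derived date, wording in these sections, one sensitivity analysis and possibly a date field for proxy or record review. Visit and phone-call dates already feed the date of last contact.

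The downsides are slightly less person-time and possibly a few late events outside the main analysis. At 10% DE / 5% ASA with 60% surfacing, that is 0.6 × 9.5 = 5.7 strokes; power with 347.3 events is 91.4% instead of 91.8%. Informative loss is reduced, not removed. If affected patients have 1.5 times the stroke hazard and the true HR is 1.00, the error in the HR falls from 2.7% to 0.8% (10% / 5%) or from 0.6% to 0.2% (2% / 1%).

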7. PLANNED ANALYSIS

For End-Of-Text (EoT) tables, the set of summary statistics is: N / Mean / SD / Min / Median / Max.

For tables that are provided for endpoints with some extreme data, median, quartiles and percentiles should be preferred to mean, standard deviation, minimum and maximum.

Tabulations of frequencies for categorical data will include all possible categories and will display the number of observations in a category as well as the percentage (%) relative to the respective treatment group (unless otherwise specified, all patients in the respective patient set whether they have non-missing values or not). Percentages will be rounded to one decimal place. The category missing will be displayed only if there are actually missing values.

When composite endpoints are evaluated as survival endpoints, the time to first onset date of any of the events listed in the composite endpoint will be used as the date of the event. For combined endpoints of non-fatal and fatal events, the time to the first event is taken. If the fatality is the first event, then the time to death (not the time to the event leading to death) is taken. For example, if a patient has a stroke at study day 100 and subsequently dies due to stroke (as adjudicated) on day 110. For the combined endpoint “Non-fatal stroke, non-fatal MI, CV death” the day of event would be day 110. In the analysis of stroke this patient enters the analysis with day 100; in an analysis of fatal stroke this patient should also be included with day 100. However in an analysis of CV death the relevant day is day 110.

7.1 DEMOGRAPHIC AND OTHER BASELINE CHARACTERISTICS

Only descriptive statistics by treatment group (and total) are planned for this section of the report.

7.2 CONCOMITANT DISEASES AND MEDICATION

Only descriptive statistics are planned for this section of the report. The frequency [N (%)] of patients with different concomitant diseases (baseline conditions) will be presented.

Concomitant medications of special interest will be collected for the following categories: antiplatelet medications, thrombolytic agents (fibrinolytics), novel direct oral anticoagulants, parenteral anticoagulants, vitamin K antagonists, GPIIb/IIIa antagonists, therapies for bleeding management. These medications will be classified using the World Health Organization (WHO) dictionary.

The remainder of concomitant medications will be collected by tickbox. All concomitant medications will be summarized according to category and displayed by treatment using descriptive statistics [N, (%)]. Separate tables for baseline, on-treatment, and post-treatment will be presented. Concomitant therapy during the treatment period will be indicated as used if used for at least one day during the treatment period (from the first on-treatment visit through termination of trial medication visit). A separate post-treatment display will be generated summarizing use from the end of treatment until last patient contact.

7.3 TREATMENT COMPLIANCE

Descriptive statistics, N / Mean / SD / 1st percentile / Q1 (lower quartile) / Median / Q3 (upper quartile) / 99th percentile / N missing, for patient mean compliance will be presented together with the N (%) of patients with compliance < 80%, between 80 and 120% and > 120%. Compliance percentage for each patient is based on *cumulative compliance per patient* (e.g., by taking average of each visit and weighting by the number of days between visits).

7.4 PRIMARY ENDPOINTS

The primary endpoint of time to first recurrent stroke (ischemic, hemorrhagic, or unspecified) as determined by the adjudication committee will be analyzed using the Cox proportional hazards regression model. Covariates included in the model will be age (binary, < or ≥ 75 years old), renal impairment (binary; creatinine clearance < or ≥ 50 mL/min), and stroke or TIA prior to index stroke (binary, “yes” or “no”).

The primary analysis will be performed on the RS for the full follow-up period. Patients who discontinue study medication will be followed until the end of the trial for OEs including vital status. Patients who are lost to follow-up for vital status will be censored for the primary endpoint of recurrent stroke at the date of last contact (see [Section 6.8](#)).

The hypotheses for the primary (and key secondary endpoints) are:

$$H_0: HR_{\text{Dabigatran/ASA}} = 1 \quad \text{vs.} \quad H_a: HR_{\text{Dabigatran/ASA}} \neq 1$$

Tests will be performed at the two-sided $\alpha = 0.05$ level.

